## 2. *Exploratory Outcomes*

Behavioral data analysis (questionnaire scores): Questionnaires administered during the study assessments (FFQ, BIS-15, FCI, DEBQ, IPAQ, Handedness, SPSRQ, YFAS, BIS/BAS, PFS) were scored per each questionnaire's instructions and different subscales were created for each questionnaire (e.g. DEBQ restrained eating subscale). Subscale scores were examined via graphical analyses (e.g. histogram, Q-Q plot) and analyzed to assess the normality of the data. Data transformation of continuous variables were used as necessary. Model assumptions and potential outliers were analyzed with various modeling diagnostics and plotting techniques. Data from pre- and post-intervention subscale scores are analyzed using PROC MIXED implemented in SAS (Version 9.4, Cary, NC). All available data from those completing the pre- and post-intervention behavioral assessments (separate from the scan assessments) are used in the analysis. Outcome variables assessed via the different questionnaires and included in the analysis are: DEBQ restrained eating, FFQ average daily total kcal consumed, FFQ percent of daily kcal from fat, FFQ percent for daily kcal from sugar, BIS-15 total impulsivity, FCI total food craving score, SPSRQ sensitivity to punishment, SPSRQ sensitivity to reward, BIS/BAS behavioral approach score, BIS/BAS behavioral inhibition score, PFS total score, YFAS total score, IPAQ total physical activity MET. Each of the outcome variables is entered into 2x2 repeated measure mixed models, including group-by-time interactions. Control variables of no interest to be included are BMI, assigned flavor, and gender. Interactions are probed for pairwise comparisons using least-squared mean comparisons, specifically of a priori contrasts of interest: between-group baseline differences and follow-up differences, and within-assignment change from pre- to post-intervention. Bonferroni-adjusted two-tailed  $p$ -values less than 0.05 are considered significant.

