**Study Session Flow:**

- Consent
- FMRI screening sheet
- Height and weight
- Internal state ratings (hunger/fullness/thirst/nausea) using visual analog scales (VAS)
- Taste test & hedonic VAS
- Surveys: FFQ, BIS-15, FCI, DEBQ, IPAQ, Handedness, SPSRQ, YFAS, BIS/BAS, PFS, Demographics
- Stop signal task
- Saliva sample
- Compensation

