**4. Post-intervention Scan Visit**

**Occurs:** 2-5 days after the end of the intervention

**Location:** Biomedical Research Imaging Center (BRIC)

**Duration:** 2 hours

**Compensation:** \$80

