**5. Post-intervention Behavioral Visit**

**Occurs:** 1-3 days after the post-intervention scan visit.

**Location:** Neuropsychology of Ingestive Behavior Lab

**Duration:** 1 hours

**Compensation:** \$60

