**Study Session Flow:**

- Weight
- Internal state ratings (hunger/fullness/thirst/nausea) using visual analog scales (VAS)
- Taste test & hedonic VAS
- Ad libitum beverage distribution
- Surveys: FFQ, YFAS, BIS-15, FCI, PFS, DEBQ, IPAQ
- Stop signal task
- Compensation

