**G. Study Evaluations and Measurements**

Demographics and Anthropometrics. Self-ported gender, race, and ethnicity were recorded. Height was measured to the nearest mm using a stadiometer. Weight was assessed to the nearest 0.1 kg using digital scales, with participants wearing light clothing without shoes at each assessment. BMI ( $\text{kg}/\text{m}^2$ ) was then calculated.

Intervention beverages & logos. To optimally test the hypothesized sugar-contingent neuroadaptations, the active SSB condition contained 111 kcals and 27g of sugar/10 fl oz (equivalent to the caloric and sugar density of soft drinks), and the unsweetened control beverages used in the study were similarly flavored to SSBs. In a preliminary study, we performed an evaluation of 6 differently mixed fruit flavors of beverages presented in the SSB and unsweetened versions to ensure that the selected beverages are equal in palatability and novelty across flavors. For the pilot, young adults meeting the inclusion criteria proposed here ( $n=27$ ;  $\bar{x}$  BMI =  $23.3 \pm 3.5$ ) rated the mixed fruit strawberry lemonade and mixed fruit cherry orange flavors as equally palatable across flavors, and equally willing to consume daily for 3 weeks in both the SSB and unsweetened versions ( $p's=0.77-0.99$ ). These ratings were not significant impacted by gender or BMI ( $p's=0.46-0.99$ ). Beverages did not include high fructose corn syrup or artificial sweeteners, or preservatives; they are caffeine- and texture-free and generally novel in flavor. Beverages were presented in 10 fl oz bottles (295 mL). To mimic the branding of the beverages, logos were placed on the beverages that correspond with flavors. Logos were selected to be novel, of similar visual complexity, in black and white, and convey no information beyond a unique symbol, and yet be easily distinguishable from one another.

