#### Acute and Habitual Dietary Intake

Participants will complete our adapted version of the Block Food Frequency Questionnaire (Block FFQ) which inquires about the frequency of consumption of 60 specific foods over the past 2 weeks (29) to measure habitual dietary intake. Food frequency questionnaires are the most practical and economical method for collecting dietary intake data in large studies (30). Block FFQ values correlated ( $r = .57$ ) with 4-day food record estimates for energy and most

nutrients (31). We have successfully used this version in previous studies (NORC5-34387, HHSN275201300015C) and published results.

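### The post-intervention FFQ window overlaps the intervention, so its kcal, sugar and fat outcomes may count the assigned drink as diet; SAP B.2 should name the target and report both bounds

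*SAP*

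**What the plan says.** SAP B.2 lists three FFQ outcomes among its exploratory questionnaire measures: "FFQ average daily total kcal consumed, FFQ percent of daily kcal from fat, FFQ percent for daily kcal from sugar". Each goes into a 2x2 repeated-measures mixed model with a group-by-time term, after scoring by the instrument's own rules.

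Protocol G (Acute and Habitual Dietary Intake) describes an adapted Block FFQ covering the "frequency of consumption of 60 specific foods over the past 2 weeks". Its stated purpose is to capture habitual diet. It is given at the pre-intervention behavioral visit (Protocol F.1: "Surveys: FFQ, BIS-15, FCI, DEBQ, IPAQ, Handedness, SPSRQ, YFAS, BIS/BAS, PFS, Demographics") and at the post-intervention behavioral visit (Protocol F.5: "Surveys: FFQ, YFAS, BIS-15, FCI, PFS, DEBQ, IPAQ").

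The post-intervention scan is held "2-5 days after the end of the intervention" (Protocol F.4), and the behavioral visit "1-3 days after the post-intervention scan visit" (Protocol F.5). Participants take one bottle a day for 21 days. Protocol G states that "the active SSB condition contained 111 kcals and 27g of sugar/10 fl oz"; the control drink is unsweetened.

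Neither document tells participants to leave the study drink out of the FFQ, tells the analyst to remove it, or says whether the outcome means total intake or non-study diet.

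**The concern.** The baseline FFQ window comes before daily dosing. The post-intervention window contains intervention days, on which one arm was handed a sugared bottle and the other was not. Any study drink entered on the form therefore appears in one arm at one time point, which is the contrast that the group-by-time term estimates.

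Two misreadings become possible. A rise in total kcal or sugar share in the SSB arm could be the assigned bottle and nothing else. Conversely, a real fall in other intake (compensation) could be cancelled by the drink and go unseen. For an instrument meant to describe habitual diet, either would mislead.

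**Working it through.** **Plan's own figure.** The SAP gives no size or power figure for the FFQ outcomes. Its only such figure (SAP A: N = 123, alpha 0.05, power 0.80, detectable effect 0.25) is for the primary hypothesis. It reproduces as a simple two-group Cohen's f of 0.2546. It is used here only as a source for N.

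**Inputs from the documents.** Look-back 14 days; scan 2-5 days after the intervention; behavioral visit 1-3 days after the scan; one SSB a day with 111 kcal and 27 g sugar.

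**Assumptions.** Sugar at 4 kcal/g, so 27 × 4 = 108 kcal; control drink about 0 kcal; full adherence; drink fully reported and not offset by eating less; background diet of 2,000 kcal/day with 15-20% of kcal from sugar and 35% from fat.

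**Step 1: overlap.** Gap = 2 + 1 = 3 to 5 + 3 = 8 days. Intervention days in the window = 14 − gap, so 11 down to 6 (79% to 43%). There are 4 × 3 = 12 permitted combinations of the two visit gaps:

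| Gap (days) | Combinations | Intervention days of 14 |
|---|---|---|
| 3 | 1 | 11 |
| 4 | 2 | 10 |
| 5 | 3 | 9 |
| 6 | 3 | 8 |
| 7 | 2 | 7 |
| 8 | 1 | 6 |

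Nine combinations give more than half, two exactly half, and one less than half. If the visit day is not counted in the look-back, each overlap rises by one day (7 to 12).

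**Step 2: drink content in the daily average.** Content × overlap/14:

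- Energy: 111 × 6/14 = 47.6 kcal/day; 111 × 11/14 = 87.2 kcal/day. With the visit day not counted: 55.5 to 95.1.
- Sugar: 27 × 6/14 = 11.6 g/day; 27 × 11/14 = 21.2 g/day.
- Sugar energy: 108 × 6/14 = 46.3 kcal/day; 108 × 11/14 = 84.9 kcal/day.

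**Step 3: shift in the shares.**

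- Sugar, from 15%: (300 + 46.3)/2,047.6 = 16.9% and (300 + 84.9)/2,087.2 = 18.4%, so +1.9 to +3.4 points.
- Sugar, from 20%: (400 + 46.3)/2,047.6 = 21.8% and (400 + 84.9)/2,087.2 = 23.2%, so +1.8 to +3.2 points.
- Fat, from 35%: 700/2,047.6 = 34.2% and 700/2,087.2 = 33.5%, so −0.8 to −1.5 points.

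Over 1,600-2,500 kcal/day and 15-25% sugar, the sugar shift runs from +1.35 to +4.25 points.

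**Step 4: could the shift alone look like a finding?** Take 123 participants split evenly, a normal approximation and unadjusted two-sided p < 0.05. For total kcal, with an assumed SD of change of 700 to 300 kcal, the chance is 6% to 36%. For sugar share (2,000 kcal, 20% sugar), with an assumed SD of change of 8 to 4 points, it is 24% to 99%. The SDs are not in the documents and drive these ranges. The SAP's Bonferroni adjustment could lower them.

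**The case against.** A reader might infer that the FFQ test must show an arm effect whatever participants eat. The documents do not support that. The adapted 60-item list, its participant instructions and its scoring rules are not given, and the drink is novel with an abstract logo. It may match no item, or may not have been reported, and then the shift is zero. Even fully reported, it moves the expected group-by-time effect without guaranteeing significance.

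A reader might also infer that the window always lies mainly in the intervention. At the 8-day gap it does not.

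The strongest defence concerns the target. The outcome is named as total kcal consumed, no aim concerns diet or compensation, and the rationale is that SSBs add to energy intake. For total intake, a reported SSB is signal. This stands as a possible reading. But Protocol G gives habitual diet as the FFQ's purpose, and Protocol H asks participants to keep to their usual eating patterns, so the other reading is at least as well supported. The SAP does not choose between them.

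It is also fair to say that the mix of on- and off-intervention days follows the same visit rules in both arms, so the mix alone creates no contrast. And these are three of 13 exploratory outcomes.

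**Conclusion.** The point holds as a conditional one. By the documents' own timing, 6 to 11 of the 14 recalled days are intervention days. If the drink was reported, the SSB arm's post-intervention FFQ contains up to about 48 to 87 kcal/day and 12 to 21 g sugar/day of assigned beverage. Sugar share is the most exposed outcome, at about +2 to +3 points under the dietary assumptions above; total kcal is less sensitive, and fat share moves the other way. If the drink was not reported, nothing shifts. Because the documents do not show which applies, the planned test cannot tell a change in habitual diet from the assigned drink.

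The change is worth making because it is cheap. Aims 1-4 are not affected.

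**What to change.** In SAP B.2:

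1. State that the three FFQ outcomes are meant to describe non-study diet, or else label them as total intake including the study drink.
2. Report the three group-by-time results under two bounds: (a) as scored, which is right if the drink was not reported; (b) after subtracting assigned-beverage kcal and sugar for each participant's overlap days, which is right if it was fully reported. For (b), take overlap from visit dates and the stated drink content, with returned-bottle counts where available. Recompute the sugar and fat shares on the reduced kcal total.
3. Claim an effect on habitual diet only if it holds under both bounds.
4. Describe the recall window as part intervention and part post-intervention.

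No instruction to participants is proposed, because SAP A says collection ended in March 2020. The cost is some SAP wording and one extra run of three models. Bound (b) needs no new data, but no dated consumption log is described, so bottle counts may be incomplete. The bounds show the reporting uncertainty; they do not resolve it.

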**Study Session Flow:**

- Pre-Scan:
  - Weight
  - Blood glucose and hba1c
  - FMRI screening sheet
  - Internal state ratings (hunger/fullness/thirst/nausea) using VAS
  - Surveys: how long since last meal, menstrual cycle (if biologically female), sleep quality rating for past 2 days
- fMRI scan
- Post-Scan:
  - Taste test & hedonic VAS
  - Compensation

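### Must the four SPSRQ and BIS/BAS scores come out of the exploratory pre/post models because the protocol's visit lists show those scales only before the intervention?

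*SAP*

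**What the plan says.** SAP section B.2 first describes scoring: "Questionnaires administered during the study assessments (FFQ, BIS-15, FCI, DEBQ, IPAQ, Handedness, SPSRQ, YFAS, BIS/BAS, PFS) were scored". It then lists 13 outcome variables, including "SPSRQ sensitivity to punishment, SPSRQ sensitivity to reward, BIS/BAS behavioral approach score, BIS/BAS behavioral inhibition score". On the data source it says: "All available data from those completing the pre- and post-intervention behavioral assessments (separate from the scan assessments) are used in the analysis". On the model: "Each of the outcome variables is entered into 2x2 repeated measure mixed models, including group-by-time interactions". The planned contrasts are "between-group baseline differences and follow-up differences, and within-assignment change from pre- to post-intervention". No outcome is set apart as measured at baseline only.

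The protocol's Section F gives the survey lists by visit:

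- Pre-intervention behavioral visit (F.1): "Surveys: FFQ, BIS-15, FCI, DEBQ, IPAQ, Handedness, SPSRQ, YFAS, BIS/BAS, PFS, Demographics".
- Post-intervention behavioral visit (F.5): "Surveys: FFQ, YFAS, BIS-15, FCI, PFS, DEBQ, IPAQ".
- Both scan visits (F.2 and F.4): "Surveys: how long since last meal, menstrual cycle (if biologically female), sleep quality rating for past 2 days".
- Intervention visits (F.3): state ratings, the beverage, a taste test and bottle exchange, with no questionnaires.

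No list after F.1 names the SPSRQ or BIS/BAS. The BIS-15 in the F.5 list is the Barratt impulsivity scale, a different instrument.

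**The concern.** A model of change needs two time points. B.2 takes its data from the behavioral visits, so F.5 is where the second one should appear, and F.5 omits both scales. The F.5 list does contain every other instrument that supplies an outcome, so the omission looks specific to these two and not like general looseness. Both documents carry the date January 25, 2023, so neither can be taken to supersede the other.

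If the F.5 list is right, the SAP announces four analyses that could never be done. A reader who later found them missing from the results could not tell whether they had been dropped selectively or never measured. That would be a reporting problem, confined to exploratory scores.

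**Working it through.** No sample-size or power figure bears on this point, so there is no stated figure to reproduce. The check compares lists and then asks what the model can estimate.

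**1. Lists.** F.1 has 11 surveys and F.5 has 7. On F.1 but not F.5: Handedness, SPSRQ, BIS/BAS, Demographics (11 − 7 = 4). Handedness and Demographics supply no B.2 outcome.

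**2. Outcomes by instrument.**

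| Instrument | B.2 outcomes | In F.1 | In F.5 |
|---|---|---|---|
| FFQ | 3 | yes | yes |
| DEBQ | 1 | yes | yes |
| BIS-15 | 1 | yes | yes |
| FCI | 1 | yes | yes |
| PFS | 1 | yes | yes |
| YFAS | 1 | yes | yes |
| IPAQ | 1 | yes | yes |
| SPSRQ | 2 | yes | no |
| BIS/BAS | 2 | yes | no |

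On both lists: 7 instruments and 3 + 6 × 1 = 9 outcomes. On F.1 only: 2 instruments and 2 + 2 = 4 outcomes. The total is 13, and 4/13 = 30.8%.

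**3. What the model can estimate.** Leaving the covariates aside, write the mean as b0 + b1·g + b2·t + b3·g·t, with g = 0 or 1 for arm and t = 0 or 1 for time. The planned contrasts are:

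- baseline difference: b1
- follow-up difference: b1 + b3
- change within arm g = 0: b2
- change within arm g = 1: b2 + b3

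With both time points the design rows are (1,0,0,0), (1,1,0,0), (1,0,1,0) and (1,1,1,1). The rank is 4 of 4 and everything is estimable. With t = 0 only, the rows are (1,0,0,0) and (1,1,0,0). The rank is 2 of 4: b0 and b1 can be estimated, b2 and b3 cannot. Three of the four contrasts and the interaction are lost.

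**4. Could a false result slip through?** No. With one time point there is no follow-up mean to compare, so the analyst meets the problem as soon as the model is run. The multiple imputation in SAP section B.1 is described for the stop-signal and VAS data; B.2 does not mention it and relies on people who completed both behavioral visits. The plan therefore has no step that would fill in a time point nobody has.

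**5. The two possible states of the data.**

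- *Follow-up scores exist.* All 13 models run as written, and the only slip is in F.5.
- *Follow-up scores do not exist.* Nine models run and four cannot, whether or not the SAP says so.

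In both cases the estimates for the nine other outcomes are the same with or without an edit to the text.

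**6. How much weight the visit lists bear.** Section F is headed as an outline and is incomplete elsewhere. Table 1 marks ad lib intake before the intervention and height after it, and the matching Section F lists omit both. Silence in other places settles nothing either: Section G does not describe the YFAS, yet the YFAS is on both behavioral-visit lists.

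**The case for a change.** The strongest case for acting is that the fix is cheap and the conflict is plain. The F.5 list follows its own order, so it does not read as a truncated copy of F.1, and the other two items it drops are natural one-time measures. The scoring sentence in B.2 repeats the F.1 order exactly, without Demographics, which suggests it was carried over from the pre-intervention visit. One look at the dataset would remove the doubt about selective reporting.

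Much of this stands. The lists do conflict, the counts are right, and no sentence in either document says the two scales were given after the intervention. The order argument is weaker. It concerns the sentence on scoring, whereas the list of outcomes is in a different order, picks particular subscales and leaves out Handedness, so it was evidently edited. A SAP dated nearly three years after collection ended that names these scores as pre/post outcomes is also some evidence, though not proof, that follow-up scores exist.

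A second objection concerns multiplicity. B.2 applies a Bonferroni adjustment without naming the family. The natural reading is the contrasts within each model, and then losing four models leaves the other nine untouched. If the family spanned outcomes, its size would matter: 0.05/13 = 0.0038 against 0.05/9 = 0.0056. The text does not favor that reading, since the adjustment follows directly on the pairwise comparisons, and the results at issue would still be exploratory.

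**Conclusion.** The inconsistency is genuine and small: 4 of 13 exploratory scores, from 2 of 9 instruments. It does not call for a change to the plan. Whether the four models can be fitted depends on data already collected and not on the wording, and an analyst will find out on opening the file. If the follow-up scores are absent, the sensible course is the only one available: the four serve as baseline measures and the other nine go ahead. Aims 1 to 4 do not use these scores, and neither does the SAP's sensitivity calculation.

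The conclusion rests on two assumptions: that the Bonferroni adjustment applies within each model, and that B.2 is run without imputation, as written. It does not depend on which list is correct, which the documents leave open.
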